### 7.3. MISSING DATA

Missing data will not be imputed. For the handling of partial or missing AE start dates, refer to APPENDIX 2: Partial Date Conventions.

### 7.4. MULTIPLE COMPARISONS/MULTIPLICITY

There will be no adjustment for multiplicity to control the Type 1 error rate over the two tests associated with the primary efficacy endpoint. The rationale for not performing this adjustment is related to the fact that the tests pertain to efficacy assessments of two unrelated vaccines (H4:IC31 and BCG). If these two evaluations were performed in two separate trials then no adjustment for multiplicity would be made. Thus, one should not be compelled to adjust for this multiplicity simply because the two evaluations are performed administratively in a single trial.

---

Document: Aeras\_C-040-404\_SAP\_V2\_0

Author: [name]

Version Number:

2.0

Version Date:

29SEP2017

Template No: CS\_TP\_BS016 – Revision 3

Reference: CS\_WI\_BS005

Effective Date: 01May2012

Copyright © 2012 Quintiles Transnational Corp. All rights reserved.

The contents of this document are confidential and proprietary to Quintiles Transnational Corp. Unauthorized use, disclosure or reproduction is strictly prohibited.

In addition, this is considered an intermediate test of biological effect study in the development of the vaccine and no definitive claims are being sought.

Multiplicity adjustment for immunology data will be performed by means of the Holm (Step-Down Bonferroni) method.

## 7.5. EXAMINATION OF SUBGROUPS

No subgroup analyses will be performed.

## 8. OUTPUT PRESENTATIONS

APPENDIX 1: Programming Conventions for Outputs describes the conventions for presentation of data in the TLFs.

The TLF shells provided together with this SAP describe the presentations for the final analysis and therefore the format and content of the TLFs to be provided by QuintilesIMS Biostatistics.

Note that verbatim terms, specifications (for example the reason a specific assessment was not done) and all variables in the TLF shells that contain the suffix (eCRF) contain verbatim text that may include spelling mistakes. Verbatim text will be presented in the listings 'as is' and no manual 'hard-coding' corrections of such data will be made.

For table presentations, the following treatment groups and cohorts will be presented:

- Treatment Group:
  - o Placebo.
  - o H4:IC31.
  - o BCG.
  - o Total.
- Cohort (if applicable):
  - o All participants.
  - o Safety and Immunogenicity Cohort.
  - o Correlates Cohort.

## 9. DISPOSITION AND PREMATURE DISCONTINUATION

All participants who provide informed consent and were randomized to a treatment group and cohort will be accounted for in this study.

Participant disposition will be presented for the Randomized analysis set (unless otherwise specified).

The following tables are planned for presentation:

- Randomization by site.
- Participant disposition and primary reason for premature study discontinuation.

---

Document: Aeras\_C-040-404\_SAP\_V2\_0  
Author: [name]

Version Number: 2.0  
Version Date: 29SEP2017

Template No: CS\_TP\_BS016 – Revision 3  
Effective Date: 01May2012

Reference: CS\_WI\_BS005

- Participant disposition and primary reason for premature treatment discontinuation (Safety analysis set).
- Protocol deviations.
- Analysis sets.

The following listings are planned for presentation:

- Participant disposition.
- Protocol deviations.
- Inclusion and/or exclusion exceptions at Study Day 0.
- Analysis sets.

The following variable will be collected at Screening on the System Enrollment eCRF:

- InForm participant number (12-digit):
  - o First three digits are the standard study indicator ('044').
  - o Next four digits are the study site indicator followed by a dash ('002-' or '014-').
  - o Last five digits are a sequential participant number (00001 to 03000), uniquely assigned per participant.

The following disposition variables, as presented in the planned TLF shells, will be collected at Screening on the Informed Consent/Cohort Assignment eCRF:

- Date of informed consent.
- Date of informed assent.
- Date of randomization.

The following disposition variables, as presented in the planned TLF shells, will be collected during the study on the Disposition Study eCRF:

- Whether the participant completed the study:
  - o Yes.
  - o No.
- Primary reason for premature study discontinuation:
  - o Lost to follow-up.
  - o Withdrew consent.
  - o Death.
  - o Adverse Event.
  - o Protocol deviation.
  - o Study terminated by sponsor.
  - o Other (specify).
- Date of study completion/premature discontinuation.

The following disposition variables, as presented in the planned TLF shells, will be collected during the study on the Disposition Treatment eCRF:

- Whether the participant completed study treatment:
  - o Yes.
  - o No.

---

Document: Aeras\_C-040-404\_SAP\_V2\_0

Author: [name]

Version Number:

2.0

Version Date:

29SEP2017

Template No: CS\_TP\_BS016 – Revision 3

Reference: CS\_WI\_BS005

Effective Date: 01May2012

Copyright © 2012 Quintiles Transnational Corp. All rights reserved.

The contents of this document are confidential and proprietary to Quintiles Transnational Corp. Unauthorized use, disclosure or reproduction is strictly prohibited.

- Primary reason for premature study treatment discontinuation:
  - o Lost to follow-up.
  - o Withdrew consent.
  - o Death.
  - o Adverse Event (specify).
  - o Protocol deviation.
  - o Study terminated by sponsor.
  - o Physician decision (specify).
  - o Other (specify).
- Date of treatment completion/premature discontinuation.

The following variable will be collected on the Exposure eCRF:

- Date of study vaccination(s).

The following protocol deviation variables, as presented in the planned TLF shells, will be collected throughout the study on the Protocol Deviations eCRF:

- Visit to which the protocol deviation is relevant.
- Protocol deviation category:
  - o Informed consent not properly obtained.
  - o Did not meet inclusion criteria or met exclusion criteria but entered in the study.
  - o Developed withdrawal criteria during the study but not withdrawn.
  - o Study vaccine dosing deviation.
  - o Procedure(s) performed out of window.
  - o Missed procedure(s).
  - o Unintended unblinding (not applicable to the BCG treatment group).
  - o Serious adverse event (SAE)/immediately reportable event (IRE) reporting.
  - o Other (specify).
- Date of protocol deviation.
- Protocol deviation description.

The following variables, as presented in the planned TLF shells, will be collected prior to Screening on the Inclusion/Exclusion Criteria (IE) eCRF and collected at Day 0 on the Eligibility Verification (IEV) eCRF:

- Category:
  - o Inclusion.
  - o Exclusion.
- Criterion number.
- Date of criterion exception noted.

The following study visit variable, as presented in the planned TLF shells, will be collected throughout the study on the Date of Visit eCRF:

- Date of visit.

---

Document: Aeras\_C-040-404\_SAP\_V2\_0

Author: [name]

Version Number:

2.0

Version Date:

29SEP2017

Template No: CS\_TP\_BS016 – Revision 3

Reference: CS\_WI\_BS005

Effective Date: 01May2012

Copyright © 2012 Quintiles Transnational Corp. All rights reserved.

The contents of this document are confidential and proprietary to Quintiles Transnational Corp. Unauthorized use, disclosure or reproduction is strictly prohibited.

The following variables, as presented in the planned TLF shells, will be imported from an Aeras approved EXCEL spreadsheet created for the review of major protocol deviations as well as inclusion of participants in each analysis set:

- For each analysis set, included in analysis set (refer to Section 5: Analysis Sets for relevant analysis sets and definitions):
  - o Yes.
  - o No.
- For each analysis set, reason(s) for exclusion from analysis set (refer to Section 5: Analysis Sets for possible reasons for exclusion from each analysis set).

## 9.1. DERIVATIONS

Based on the aforementioned, the following variables, as presented in the planned TLF shells, will be derived:

- Treatment unblinded:
  - o Based on unintended unblinding on the Protocol Deviation eCRF.
- Update the InForm participant number to the participant ID (8-digit):
  - o Replace four digits from digit 4 to 7 with the 3-digit study site number, by removing the first digit ('002-' → '02-' and '014-' → '14-').
  - o Last five digits kept as is.  
This participant ID will be used in all the listings, as presented in the relevant TLF shells.
- Total number of doses:
  - o Per participant, determine the number of doses received.
  - o If date of vaccination is available, the vaccination will be considered as administered.
- Age (years), sex, race:
  - o Refer to Section 10: Demographic and Other Baseline Characteristics and Section 10.1: Derivations for details.

## 10. DEMOGRAPHIC AND OTHER BASELINE CHARACTERISTICS

No inferential statistical testing will be performed for demographic or other Baseline characteristics.

The following table is planned for presentation (based on the Safety analysis set):

- Demographics and other Baselines characteristics.
  - o Presented by means of the default summary statistics for quantitative and qualitative variables.
  - o Percentage (%) of participants will be calculated relative to the total number of participants in the Safety analysis set per treatment group with data available (observed case).
  - o This table will be repeated for the Modified Intent-to-treat analysis set, Per Protocol analysis set as well as the Safety and Immunogenicity Cohort (Safety analysis set).

The following listing is planned for presentation (based on the Randomized analysis set):

- Demographics and other Baseline characteristics.

---

Document: Aeras\_C-040-404\_SAP\_V2\_0

Author: [name]

Version Number:

2.0

Version Date:

29SEP2017

Template No: CS\_TP\_BS016 – Revision 3

Reference: CS\_WI\_BS005

Effective Date: 01May2012

Copyright © 2012 Quintiles Transnational Corp. All rights reserved.

The contents of this document are confidential and proprietary to Quintiles Transnational Corp. Unauthorized use, disclosure or reproduction is strictly prohibited.

The following demographic variables, as presented in the planned TLF shells, will be collected at Screening on the Demography eCRF:

- Date of birth.
- Sex:
  - Male (M).
  - Female (F).
- Race:
  - Asian.
  - Black.
  - White.
  - Coloured.
  - Other (specify).

The following variable, as presented in the planned TLF shells, will be collected at Screening on the Informed Consent/Cohort Assignment eCRF:

- Cohort assignment:
  - Safety and Immunogenicity Cohort.
  - Correlates Cohort.

The following demographic variable, as presented in the planned TLF shells, will be collected at Screening on the School Selection eCRF:

- School:
  - Drostdy.
  - Esselenpark Sekondêr.
  - Hexvallei Hoërskool.
  - Hexvallei Sekondêr.
  - Hoërskool Breërivier.
  - HS Goudini.
  - Montana Hoërskool.
  - Van Cutsem.
  - Vusisizwe.
  - Worcester Gimnasium.
  - Worcester Sekondêr.
  - Other (specify).

The following demographic variable, as presented in the planned TLF shells, will be collected at Screening on the Region Selection eCRF:

- Region:
  - Athlone.
  - Gugulethu.
  - New Crossroads.
  - Nyanga.
  - Old Crossroads.
  - Philippi East.
  - Philippi West.
  - Other (specify).

---

Document: Aeras\_C-040-404\_SAP\_V2\_0

Author: [name]

Version Number:

2.0

Version Date:

29SEP2017

Template No: CS\_TP\_BS016 – Revision 3

Reference: CS\_WI\_BS005

Effective Date: 01May2012

Copyright © 2012 Quintiles Transnational Corp. All rights reserved.

The contents of this document are confidential and proprietary to Quintiles Transnational Corp. Unauthorized use, disclosure or reproduction is strictly prohibited.

The following Baseline characteristic, as presented in the planned TLF shells, will be collected on the Height and Weight eCRF:

- Baseline body mass index (BMI) (kg/m^2).

## 10.1. DERIVATIONS

Based on the aforementioned the following variable, as presented in the planned TLF shells, will be derived:

- Age (years):
  - o Calculated relative to the reference start date (Day 0 vaccination).
  - o Age (years) = (date of Day 0 vaccination) – (date of birth)/365.25.

All listings, as presented in the relevant TLF shells, will include the following demographic information:

- Age (years).
- Sex.
- Race.

These demographic variables will be concatenated to form one demographic variable in the following format:

- Age (years)/Sex/Race:
  - o For example: 17/M/WHITE.

## 11. MEDICAL HISTORY

Medical History will be presented for the Randomized analysis set.

The following listing is planned for presentation:

- Medical history.

Medical history will be coded using Medical Dictionary for Regulatory Activities (MedDRA) Version 16.1.

The following medical history variables, as presented in the planned TLF shells, will be collected on the Medical History (MH) and Interval Medical History (IMH) eCRFs during the study:

- Verbatim term (eCRF).
- Date started.
- Date stopped or ongoing.
- Comment (eCRF).

The following medical history coding variables, as presented in the planned TLF shells, will be included in the data transfers received from Data Management:

- System Organ Class.
- Preferred Term.

---

Document: Aeras\_C-040-404\_SAP\_V2\_0

Author: [name]

Version Number:

2.0

Version Date:

29SEP2017

Template No: CS\_TP\_BS016 – Revision 3

Reference: CS\_WI\_BS005

Effective Date: 01May2012

Copyright © 2012 Quintiles Transnational Corp. All rights reserved.

The contents of this document are confidential and proprietary to Quintiles Transnational Corp. Unauthorized use, disclosure or reproduction is strictly prohibited.

No imputation of partial or missing dates will be performed for medical history and study days will not be presented for these cases.

## 12. PRIOR AND CONCOMITANT MEDICATIONS

Concomitant medications will be presented for the Randomized analysis set.

The following listing is planned for presentation:

- Concomitant medications.

Concomitant medication will be coded with World Health Organization – Drug Dictionary (WHO-DD) Version 01DEC2013.

The following concomitant medication variables, as presented in the planned TLF shells, will be collected on the Prior and Concomitant Medication (CM) eCRF:

- Verbatim term (eCRF).
- Date started.
- Date stopped or ongoing.
- Dose and unit per administration.
- Frequency.
- Route of administration.
- Indication.

The following medication coding variables, as presented in the planned TLF shells, will be included in the data transfers received from Data Management:

- Preferred Term.
- Anatomical Therapeutic Chemical (ATC) Level 1 term.
- ATC Level 3 term.

No imputation of partial or missing dates will be performed for medications and study days will not be presented for these cases.

## 13. STUDY VACCINATION

Administration of the study vaccine(s) will be presented for the Safety analysis set.

The following table is planned for presentation:

- Study vaccination administration:
  - o Presented by treatment group by means of the default summary statistics for qualitative variables.
  - o Percentage (%) of participants will be calculated relative to the total number of participants in the Safety analysis set per treatment group.

---

Document: Aeras\_C-040-404\_SAP\_V2\_0  
Author: [name]

Version Number: 2.0  
Version Date: 29SEP2017

Template No: CS\_TP\_BS016 – Revision 3  
Effective Date: 01May2012

Reference: CS\_WI\_BS005

- o The number and percentage (%) of participants who received all scheduled vaccinations will be presented.
- o The number and percentage (%) of participants who received the second vaccination within the protocol-defined window will be presented. The denominator for the % will be based on the total number of participants in the Safety analysis set per treatment group (excluding BCG).

The following listing is planned for presentation (based on the Randomized analysis set):

- Study vaccination administration.

Study vaccinations will be administered on the study days as specified for each treatment group in Table 1: Planned Enrollment by Treatment Group and Cohort.

The following exposure variables, as presented in the planned TLF shells, will be collected on the Exposure Day 0 and Exposure Day 56 eCRFs:

- Study vaccination administered:
  - o Yes.
  - o No.
- Date and time of study vaccination.
- Full volume administered:
  - o Yes.
  - o No.
- Location (arm):
  - o Left.
  - o Right.

The following treatment deviation variables, as presented in the planned TLF shells, will be collected in collaboration with the clinical trial manager (CTM) with the Aeras/Quintiles Process Instruction: Treatment Deviation Identification and Authorization document:

- In accordance with randomization:
  - o Yes.
  - o No.
- Out of study window:
  - o Yes.
  - o No.

## 13.1. DERIVATIONS

Based on the aforementioned the following variables, as presented in the planned TLF shells, will be derived:

- Participants who received all scheduled vaccinations:
  - o Yes:
    - For BCG treatment group participants if Day 0 study vaccination date is available.
    - For H4:IC31 or Placebo treatment group participants if Day 0 and Day 56 study vaccination dates are both available.

---

Document: Aeras\_C-040-404\_SAP\_V2\_0

Author: [name]

Version Number:

2.0

Version Date:

29SEP2017

Template No: CS\_TP\_BS016 – Revision 3

Reference: CS\_WI\_BS005

Effective Date: 01May2012

Copyright © 2012 Quintiles Transnational Corp. All rights reserved.

The contents of this document are confidential and proprietary to Quintiles Transnational Corp. Unauthorized use, disclosure or reproduction is strictly prohibited.

- o No:
  - For BCG treatment group participants if Day 0 study vaccination date is not available.
  - For H4:IC31 or Placebo treatment group participants if Day 0 and/or Day 56 vaccination dates are not available.
- Study day of the Day 56 vaccination:
  - o Calculated relative to Day 0 vaccination (refer to Section 6.1: Reference Start Date and Study Day).
- Participants who received the second vaccination within the protocol-defined window:
  - o This is only applicable to the H4:IC31 and Placebo participants.
  - o The allowable window for the Day 56 visit is 56-2 days until 56+14 days from the Day 0 vaccination.
  - o Yes:
    - Study day of the Day 56 vaccination  $\geq 54$ .
  - AND
  - Study day of the Day 56 vaccination  $\leq 70$ .
  - o No:
    - Study day of the Day 56 vaccination  $< 54$ .
  - OR
  - Study day of the Day 56 vaccination  $> 70$ .

## 14. EFFICACY OUTCOMES

### 14.1. PRIMARY EFFICACY

#### 14.1.1. PRIMARY EFFICACY ENDPOINT

The primary efficacy endpoint is defined as QuantiFERON TB Gold-in-tube (QFT-GIT) conversion, at any time point after Day 84 through end of follow-up, from negative at Screening to positive, using the manufacturer's recommended threshold of  $\geq 0.35$  IU/mL.

#### 14.1.2. ANALYSIS OF PRIMARY EFFICACY ENDPOINT

The following tables will be presented for the Modified Intent-to-treat analysis set:

- QFT-GIT results at each visit:
  - o Number and percentage (%) of participants in each category per visit:
    - Negative.
    - Positive.
    - Missing.
  - o Percentage (%) of participants will be calculated relative to the total number of participants in the Modified Intent-to-treat analysis set who have QFT-GIT assessments available per treatment group per visit.

---

Document: Aeras\_C-040-404\_SAP\_V2\_0

Author: [name]

Version Number:

2.0

Version Date:

29SEP2017

Template No: CS\_TP\_BS016 – Revision 3

Reference: CS\_WI\_BS005

Effective Date: 01May2012

Copyright © 2012 Quintiles Transnational Corp. All rights reserved.

The contents of this document are confidential and proprietary to Quintiles Transnational Corp. Unauthorized use, disclosure or reproduction is strictly prohibited.

- Compliance to QFT-GIT testing:
  - o Number and percentage (%) of participants in each compliance category per visit:
    - Yes.
    - No.
    - Missing.
  - o Percentage (%) of participants will be calculated relative to the total number of participants in the Modified Intent-to-treat analysis set expected to have a QFT-GIT assessment available per treatment group per visit (N1).
- QFT-GIT conversion rates, primary endpoint (therefore endpoints occurring after Day 84):
  - o Number and percentage (%) of participants in each conversion status category:
    - Yes.
    - No.
    - Missing.
  - o Hazard ratio (H4:IC31/comparator) presented:
    - Point estimates (based on the Cox regression model).
    - P-values for the comparison of the estimated hazard ratios of QFT-GIT conversion based on a one-sided log-rank test.
      - H4:IC31 versus Placebo.
      - BCG versus Placebo.
      - H4:IC31 versus BCG (at the request of the sponsor's partner).
  - o Vaccine efficacy presented:
    - Point estimate (based on the hazard ratio estimates).
    - 80% two-sided CI based on the hazard ratio estimate from the Cox regression model.
  - o This table will be repeated for the Per Protocol, Adjusted Modified Intent-to-treat (First Recall Positive Omit) analysis sets. This table will also be repeated for the adjudication approach (refer to Section 3.3: Changes to Analysis from Protocol).
  - o As a sensitivity analysis the content of this table will be repeated in a separate table using interval censoring for the MITT analysis set.
- First QFT-GIT conversion by visit:
  - o Number and percentage (%) of participants with first QFT-GIT conversion at each of the scheduled visits.
  - o Number of participants at risk for first conversion at each scheduled visit.
  - o At risk defined as participants with:
    - A negative QFT-GIT result at the preceding visit without a previous positive QFT-GIT result.
    - A QFT-GIT result available at the relevant visit.
  - o This table will be repeated for the Per Protocol analysis set.
- Follow-up time until first QFT-GIT conversion:
  - o Number of participants contributing to the total follow-up time (at risk).
  - o Cumulative number of participants:
    - Censored (not due to a primary endpoint at the time of the last available non-positive QFT-GIT result).
    - With an event (primary endpoint).
  - o The total follow-up time (person-months), as measured from Randomization (1 month = 4 weeks).
  - o The Kaplan-Meier event rate presented at each relevant post-Day 84 visit.
  - o This table will be repeated for the Per Protocol analysis set.

Document: Aeras\_C-040-404\_SAP\_V2\_0

Author: [name]

Version Number:

2.0

Version Date:

29SEP2017

Template No: CS\_TP\_BS016 – Revision 3

Reference: CS\_WI\_BS005

Effective Date: 01May2012

Copyright © 2012 Quintiles Transnational Corp. All rights reserved.

The contents of this document are confidential and proprietary to Quintiles Transnational Corp. Unauthorized use, disclosure or reproduction is strictly prohibited.

- Primary endpoints by school/region:
  - o Number and percentage (%) of participants who experienced a primary endpoint in each school/region.
- Primary endpoints by site and sex:
  - o Number and percentage (%) of participants who experienced a primary endpoint in each site/sex.

The following table will be presented for the Randomized analysis set:

- QFT-GIT conversion rates including all post-Day 0 conversions:
  - o Number and percentage (%) of participants in each conversion status category:
    - Yes.
    - No.
    - Missing.
  - o Two groups of conversion time points included:
    - Any QFT-GIT conversion (early [Day 84] or post-Day 84) (at risk participants include all participants).
    - Early (Day 84) conversion (at risk participants include all participants).
  - o Hazard ratio (H4:IC31/comparator) presented:
    - Point estimates (based on the Cox regression model).
    - P-values for the comparison of the estimated hazard ratios of QFT-GIT conversion based on a one-sided log-rank test.
      - H4:IC31 versus Placebo.
      - BCG versus Placebo.
      - H4:IC31 versus BCG (included at the request of the sponsor's partner).
  - o Vaccine efficacy presented:
    - Point estimate (based on the hazard ratio estimates).
    - 80% two-sided CI based on the hazard ratio estimate from the Cox regression model.

The following figures will be presented for the Modified Intent-to-treat analysis set:

- Time on study:
  - o Kaplan-Meier plot per treatment group.
  - o Cumulative follow-up time as measured from randomization (1 month = 4 weeks).
  - o Event is defined as whichever occurs first:
    - Initial QFT-GIT conversion.
    - Early termination/study completion.
  - o This figure will be repeated for the Per Protocol analysis set.
- Time to first post-Day 84 QFT-GIT conversion, primary endpoint:
  - o Kaplan-Meier plots per treatment group for the following:
    - Time to first post-Day 84 QFT-GIT conversion.
  - o Time to first QFT-GIT conversion will be presented in months, measured from Day 84 (1 month = 4 weeks).
    - Censored (at the time of the last available non-positive QFT-GIT result).
  - o This figure will be repeated for the Per Protocol analysis set.
- Time to first post-Day 84 QFT-GIT conversion (interval-censored sensitivity analysis):
  - o Survival function estimate plot per treatment group based on a life-table analysis.
  - o Time to QFT-GIT conversion measured from Day 84.
  - o Time to conversion will be presented in 6-month intervals.

---

Document: Aeras\_C-040-404\_SAP\_V2\_0

Author: [name]

Version Number:

2.0

Version Date:

29SEP2017

Template No: CS\_TP\_BS016 – Revision 3

Reference: CS\_WI\_BS005

Effective Date: 01May2012

Copyright © 2012 Quintiles Transnational Corp. All rights reserved.

The contents of this document are confidential and proprietary to Quintiles Transnational Corp. Unauthorized use, disclosure or reproduction is strictly prohibited.

The following figure will be presented for the Randomized analysis set:

- Time to First QFT-GIT Conversion (Early or Post-Day 84):
  - o Kaplan-Meier plots per treatment group for the following:
    - Time to any QFT-GIT conversion (early or post-Day 84) measured from Day 0.
  - o Time to QFT-GIT conversion will be presented in months, measured from Randomization (1 month = 4 weeks).
    - Censored (not due to a primary endpoint at the time of the last available non-positive QFT-GIT result).

The following listing will be presented for the Randomized analysis set:

- QuantiFERON results.

The following QuantiFERON variables, as presented in the planned TLF shells, will be collected on the QuantiFERON and QuantiFERON Re-valuation eCRFs:

- Date of sample collection.
- Qualitative results:
  - o Negative.
  - o Positive.
- Quantitative Result:
  - o QFT-Nil (IU/mL).
  - o QFT-Ag (IU/mL).
  - o QFT-Mitogen (IU/mL).

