### 7.3 Prevention of Infection (QFT-GIT Conversion) Analyses

The primary *Mtb* infection endpoint will be QFT-GIT conversion from a negative to positive test, using the manufacturer's recommended threshold of 0.35 IU/mL, at any time-point after Day 84 and through end of follow-up for the primary endpoint (see below). The frequency of QFT-GIT negativity/positivity will be summarized for each treatment group at screening, on Day 84, on Month 6, and for all subsequent assessments. The log-rank statistic will be used to test the null hypothesis of no difference in the rates of *Mtb* infection over the follow-up period between each of the AERAS-404 and BCG groups compared to the placebo group. The log-rank test statistic compares estimates of the hazard functions of the vaccine groups at each observed event time. It is constructed by computing the observed and expected number of events in the groups at each observed event time and then summing these to obtain an overall summary across all time points where there is an event. As subjects convert their QFT-GIT tests over time (experience a primary endpoint) or are lost to follow up the number of subjects at risk over time will change. As this is a proof of concept study, these two log-rank tests (AERAS-404 compared to placebo and BCG revaccination compared to placebo) will be performed with a 1-sided Type 1 error of 0.1. There will be no adjustment for multiplicity to control the Type 1 error rate over the two tests. The rationale for not performing this adjustment is related to the fact that the tests pertain to efficacy assessments of two unrelated vaccines. If these two evaluations were performed in two separate trials then no adjustment for multiplicity would be made. Thus, one should not be compelled to adjust for this multiplicity simply because the two evaluations are performed administratively in a single trial.

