## 7.6 Sample Size Considerations

Sample size for the trial is based on the power to detect a reduction in the rate of infection with *Mtb*, as determined by QFT-GIT conversion. As a proof of concept study looking for evidence of biologic impact, the trial is designed to distinguish a QFT-GIT conversion rate reduction of 50% compared to placebo for each vaccine (AERAS-404 and BCG) with power of 80% and a type 1 error rate of 10% (1-sided).

Trial design calculations are performed by computer simulation. The simulations estimate the statistical operating characteristic of a conditional binomial test which, due to relative rarity of the endpoint, provides an excellent approximation to the operating characteristic of the log-rank tests which will be used in the analyses of trial data. The following assumptions, based on preliminary data from SATVI (Mahomed et al, 2011b) were used in these simulations:

- Primary *Mtb* infection endpoint rate = 10% per year
- Rate of loss to follow up = 7% per year
- Average rate of enrollment = 20 subjects per week
- Maximum duration of follow up to primary conversion = 24 months with 6-monthly study visits

Under these assumptions, a total sample size of 990 is expected to provide 64 primary QFT-GIT conversion endpoints approximately 21 months after the first subject is enrolled. Follow up will continue until 64 endpoints are accrued and a median follow up duration of 15 months for individual subjects have both occurred. A 10% rate of QFT-GIT conversions per year is conservative (SATVI data have shown an average 17% conversion rate in adolescents); however, continuing to follow subjects until the required number of endpoints is accrued ensures adequate power for the primary endpoint.

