### 2.1. PRIMARY OBJECTIVES

The primary objectives are:

- To evaluate the safety profile in human immunodeficiency virus (HIV)-uninfected, remotely Bacillus Calmette-Guérin (BCG) vaccinated adolescents of:
  - o H4:IC31 (also known as AERAS-404).
  - o BCG revaccination.
- To evaluate prevention of *Mycobacterium tuberculosis* (*Mtb*) infection, as measured by rates of conversion using a QuantiFERON Tuberculosis (TB) gold-in-tube (QFT-GIT) assay of:
  - o H4:IC31 compared to Placebo.
  - o BCG revaccination compared to Placebo.

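### The added H4:IC31-versus-BCG comparison has a one-sided p-value with no stated hypothesis or direction, and the multiplicity statement does not cover it

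*SAP*

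**What the plan says.** The protocol (7.3) sets its null hypotheses "between each of the AERAS-404 and BCG groups compared to the placebo group", and says that these two log-rank tests "will be performed with a 1-sided Type 1 error of 0.1". The SAP objectives (2.1 and 2.2) follow suit: "H4:IC31 compared to Placebo", and BCG revaccination against placebo. Protocol 7.6 powers the same two contrasts: "the trial is designed to distinguish a QFT-GIT conversion rate reduction of 50% compared to placebo for each vaccine". AERAS-404 and H4:IC31 are the same product.

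SAP 14.1.2 then specifies "P-values for the comparison of the estimated hazard ratios of QFT-GIT conversion based on a one-sided log-rank test" and lists three comparisons beneath it: the two against placebo, and "H4:IC31 versus BCG (at the request of the sponsor's partner". The third line recurs in the table of all post-Day 0 conversions (14.1.2), the 6-month sustained conversion table (14.2.2) and the end-of-study sustained conversion table (14.3.2). In each, the hazard ratio is headed as H4:IC31 over comparator. A vaccine efficacy entry follows with an 80% two-sided interval. The derivations in 14.1.3 and 14.2.3 define vaccine efficacy as one minus the ratio of vaccine to comparator, and also mention a 95% two-sided interval.

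On multiplicity, SAP 7.4 says: "There will be no adjustment for multiplicity to control the Type 1 error rate over the two tests associated with the primary efficacy endpoint". Its reasons are that the two vaccines are unrelated and could have been evaluated in separate trials, and that the study seeks no definitive claims.

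**The concern.** A one-sided test needs a reason to look in one direction only. Against placebo the reason is clear, because the trial asks whether a vaccine prevents conversion. Between two active arms either could be better, and neither document makes superiority of H4:IC31 the only result of interest. Three things follow.

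- **Tail.** The SAP does not say which tail is used. The ratio heading points to the one favouring H4:IC31. If that is what is programmed, a real BCG advantage gives a p-value near 1, which is easily read as no difference when quoted alone.
- **Label.** The vaccine-over-comparator formula is not restricted to placebo. It therefore allows one minus the hazard ratio against BCG to be printed as vaccine efficacy, although BCG is an active arm.
- **Multiplicity.** The separate-trials argument cannot extend to a head-to-head contrast, which two separate placebo-controlled trials would not provide. The third test is neither covered by 7.4 nor set aside by it.

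**Working it through.** **Inputs.** One-sided level 0.10 (Protocol 7.3), so the critical value is 1.2816. Hazard ratio 0.5 against placebo, 80% power and 64 events over all arms (Protocol 7.6). Allocation 1:1:1 (Protocol 2.2).

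**Formula.** With d events in two equal arms, the log-rank z statistic has mean sqrt(d/4) × ln(HR) and unit variance, approximately.

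**The plan's own figure.** Suppose one vaccine halves the rate and the other does nothing. The 64 events then split in the ratio 1 : 0.5 : 1, or 25.6, 12.8 and 25.6. Placebo and the effective vaccine together have 38.4. Power = Φ(sqrt(38.4/4) × 0.693 − 1.2816) = Φ(2.148 − 1.282) = Φ(0.866) = 80.7%, against 80% stated. The stated power is reproduced for the placebo comparisons.

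**H4:IC31 against BCG.** The documents give no effect size or event count for this pair, so the scenarios below are assumptions that split the 64 events in proportion to the arm rates. HR is H4:IC31 over BCG and m is the mean of z. The chance of one-sided significance favouring H4:IC31 is Φ(−1.2816 − m). The chance that the two-sided 80% interval lies wholly above 1 (BCG better) is Φ(m − 1.2816).

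| Scenario | Events in pair | HR | m | One-sided p < 0.10 for H4:IC31 | 80% interval wholly above 1 |
|---|---|---|---|---|---|
| BCG halves the rate, H4:IC31 does nothing | 38.4 | 2.0 | 2.148 | 0.03% | 80.7% |
| BCG halves the rate, H4:IC31 cuts it by a quarter | 35.6 | 1.5 | 1.209 | 0.6% | 47.1% |
| Both halve the rate | 32 | 1.0 | 0 | 10% | 10% |

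At HR 1.5 with exactly 38 events, m = sqrt(9.5) × 0.405 = 1.25 and the first probability is again 0.6%. More events at the final analysis would make it smaller still.

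**What a reader would see.** Take an observed HR of 2.0 with 38 events. The standard error of ln(HR) is 2/sqrt(38) = 0.324. The 80% interval is 2 × exp(±1.2816 × 0.324), or 1.32 to 3.03; as one minus HR it runs from −203% to −32%. The one-sided p-value favouring H4:IC31 is 0.984. The two-sided p-value is 2 × (1 − 0.984), about 0.03. The interval and the one-sided p-value would appear to disagree.

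**False positives under the global null.** The two placebo contrasts share an arm and so have correlation 0.5. The chance that at least one exceeds 1.2816 is 16.8%. Adding the third contrast, one-sided for H4:IC31 over BCG, gives 23.5% by simulation of three independent normal arm means. Treating the tests as independent would give 1 − 0.9² = 19.0% and 1 − 0.9³ = 27.1%.

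**The case against.** A reader might infer that the plan cannot show BCG to be better than H4:IC31. The documents do not support that. The same tables carry a two-sided 80% interval, and the derivations add a 95% one. A two-sided 80% interval amounts to a one-sided 0.10 test in each direction, and in the HR 2.0 scenario it would lie wholly on the BCG side with probability 80.7%. The blindness belongs to the p-value alone. For the same reason, the gap between the one-sided test and a two-sided 0.20 test is not lost power, provided the interval is printed for this contrast.

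A reader might also infer that the error rate doubles to 20% because the direction could be picked after unblinding. Nothing in the documents suggests such a choice, so that figure is hypothetical.

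The tail and the label are inferences. No section states the tail or the level for this contrast, and the program code in 14.1.3 specifies no tail. The H4:IC31-over-comparator heading is loose, since it also stands above the BCG-versus-placebo line. The three comparisons are listed under the p-value, while the vaccine efficacy entry names none. The table shells, which would settle this, are not available.

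The multiplicity consequence is limited. The comparison is not an objective, and it is openly marked as a partner's request. Protocol 7.7.2 allows the SAP to add analyses. Part of the SAP around the end of Section 3.3 was not available for review, so nothing is claimed about whether the addition is listed there.

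What stands is that a one-sided p-value is specified with no hypothesis to support it and no stated tail, and that 7.4 is silent on the comparison.

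**Conclusion.** The point holds as a minor defect of specification and labelling. H4:IC31 versus BCG has no objective, direction or power statement in either document, yet it receives a one-sided p-value in four tables. If the tail favours H4:IC31, as the heading suggests, that p-value has under a 1% chance of significance at a hazard ratio of 1.5 to 2.0 with about 38 events in the pair, and would be near 1 if BCG were clearly ahead. The size rests on the inferred tail, the normal approximation and an assumed split of the 64 planned events.

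Counting the third test moves the chance of any false positive from about 17% to 23.5%, but only if a comparison that is not an objective is placed in the primary family. The two placebo tests keep their own 10% level, and no primary conclusion changes.

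**What to change.** For H4:IC31 versus BCG only, in SAP 14.1.2, 14.2.2 and 14.3.2:

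- report the hazard ratio (H4:IC31 over BCG) with its two-sided interval and a two-sided log-rank p-value;
- label the comparison exploratory, and the estimate relative rather than vaccine efficacy;
- state in 7.4 that this comparison lies outside the two primary tests and supports no efficacy claim.

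Keep the one-sided 0.10 tests for the two placebo comparisons. The cost is a few lines of SAP text and one p-value option, with no new data. The downside is that the head-to-head p-value doubles when H4:IC31 is ahead: a one-sided 0.10 becomes 0.20.
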